14.4 Stratification Factors

Patients will be randomized in equal proportion to receive either HTIMRT or SIMRT using a permuted block design stratified by baseline PSA (<10 vs 10 to \leq 100), Gleason score (6-7 vs 8-10) and short term (4 to 6 months) androgen deprivation (STAD) therapy (Y vs. N). Where appropriate, these factors will be used in the analysis of study data; for example, to stratify statistical tests comparing treatment arms or to adjust regression models. We note that STAD therapy will be recommended for all Gleason 8 patients; however, we allow for all eight possible combinations as strata in order to ensure equal treatment allocation in the event that enrollment includes a small number of patients with uncommon combinations of these factors.

14.5 Analysis plan

The main analysis of study findings will be done by treatment assignment (intention-to-treat) in all patients who meet evaluable criteria as stated in Section 14.3. We will report any instances of treatment crossover. As noted above, analyses of some secondary endpoints, including acute toxicity, psychosocial parameters, tissue and blood product-related biomarker distribution on ultrasound-guided biopsies, and initial MRI findings may be reported before the efficacy endpoints, including the primary endpoint. These secondary endpoints will be analyzed after all planned patients have been accrued, completed treatment and have a minimal potential follow-up of 3 months from the end of RT. An initial analysis of clinical outcome (efficacy) is

planned after all patients have been assessed for two year post treatment failure status and a final analysis will be done at the completion of the planned 5 year follow up of all study patients. Statistical tests comparing treatment arms will be one-sided with 5% significance level and stratified where appropriate by the factors considered in randomization.

Statistical analysis will include descriptive statistics for patient demographics and baseline disease characteristics, both overall and by treatment arm. Counts and percentages will be used to summarize the distribution of categorical variables while median, range, mean and standard deviation will be used for continuous variables. Baseline characteristics will include age, sex, race/ethnicity, T-category, Gleason score, PSA, risk group and performance status. Biomarker measurements and proteomic/genomic profiles obtained from baseline biopsy will also be summarized with descriptive statistics. (76)

Treatment received will be summarized by the type of RT and STAD components of therapy, the number and duration of treatment delays, and the rates of discontinuation or completion. Summaries will be provided for each treatment arm. Safety analysis will include a detailed tabulation of acute and late occurring toxicity by type and grade, both overall and by treatment arm. Additionally, we will estimate the cumulative incidence (from start of treatment) of grade 2+ and 3+ genitourinary (GU) toxicity and of grade 2+ and 3+ gastrointestinal (GI) toxicity in each treatment arm. Death without the toxicity of interest will be treated as a competing risk, and toxicity rates will be compared by treatment arm using Gray's test. (77, 78)

The primary trial endpoint, two-year failure rate, will be estimated for each treatment arm as a proportion with corresponding 95% confidence interval by the exact binomial method. Comparison of the failure rate for SIMRT versus HTIMRT will be based on a one-sided Fisher's exact test at a 5% significance level. Similar estimation and comparison will be done for the biopsy failure rate among clinical/biochemical failure-free patients at the two year post RT follow up. Biopsy findings two years post RT will be further characterized as negative, atypical, carcinoma with treatment effect, or carcinoma without treatment effect and compared by treatment arm using Fisher's exact test. Biomarker and proteomic/genomic characteristics of prostate biopsy tissue obtained two-year post treatment, and changes relative to baseline, will be summarized by descriptive statistics. Change from baseline will be tested for significance using t-test (means) or McNemar's test (proportions) for paired data and comparison of changes by treatment arm will be based on two-sample tests (t-test or Fisher's exact test). (For biomarker studies, nonparametric tests or data transformations to attain approximate normal distributions will be applied as needed.) Logistic regression models adjusted for treatment will be used to investigate the association between baseline factors, including biomarkers and proteomic/genomic profiles, and biopsy failure two-years post treatment. Changes in biomarkers and proteomic/genomic characteristics will also be investigated for association with biopsy failure. (79)

Patients will be followed for disease progression and vital status for a period of five years after completing study treatment. Progression of disease will be categorized as biochemical failure (BF), clinical failure (CF), or combined (BF + CF), where combined failure refers to documented evidence of BF and CF occurring within 6 months of each other with the earlier date used. CFs will be further categorized as local, nodal, or distant. Start of subsequent therapy will be considered a failure event for selected analyses as indicated in the table below. Deaths will be categorized as related/unrelated to prostate cancer. The number of observed failures will be tabulated by treatment arm and failure type. Similarly, vital status will be tabulated by treatment arm and presence or absence of disease at last follow up.

Time to event endpoints will be analyzed by Kaplan-Meier (KM) or competing risk (CR) methods as indicated in the Table 14.5 (80, 77) Where the Kaplan Meier method is used, point estimates and 2-sided 95% confidence intervals will be reported for selected times such as 1, 2

and 5 years from treatment start using Greenwood's variance and the log-log transform method. Median event-free or overall survival time, if attained, will also be reported. Treatment arms will be compared by the log rank test. Cox regression models including treatment as a covariate will be used to explore the prognostic effect of baseline characteristics as well as biomarkers and proteomic and genomic profiles. Regression findings will be expressed as hazard ratios and corresponding 95% confidence intervals. For analyses involving competing risks, cumulative incidence rates will be reported for selected times with corresponding 2-sided 95% confidence intervals based on the variance estimator of Aalen and the log-log transform method. Treatment comparison of event rates will be based on Gray's test and regression models investigating prognostic factors will be fit by the method of Fine and Gray. (78, 81) Where study data indicate that at most a small number of competing risk events have occurred, analysis will be simplified by treating such events as censored observations in a Kaplan Meier analysis, since the resulting overestimation of the event rate will be negligible.

Table 14.5. Time-to-event endpoints.

Endpoint	Analysis	Events (earliest)	Competing risks	Censoring
Failure rate	CR	CF, BF, BF+ CF (within 6 months of each other) Start subsequent therapy Death related to prca without prior evidence of failure	Death unrelated to prca	Last clinical +PSA assessment
Toxicity rate (to be done separately for GI and GU)	CR	Onset of grade 2+ and 3+ toxicity	Start subsequent therapy Death, any cause	Last contact
Failure free survival (FFS)	KM	CF, BF, BF+ CF Start subsequent therapy Death, any cause	n/a	Last clinical or PSA assessment
Prostate cancer mortality	CR	Death related to prca	Death unrelated to prca	Last contact
Overall survival (OS)	KM	Death, any cause	n/a	Last contact

KM: Kaplan-Meier. **CR:** competing risk. **BF:** Biochemical failure. **CF:** clinical failure. **prca:** prostate cancer. **GI:** gastrointestinal. **GU:** genitourinary.

Finally, to assess the prognostic value of 2-year post treatment biopsy findings, we will further study patients who had this procedure without prior evidence of biochemical or clinical failure. Taking the date of biopsy as the start of follow up, we will analyze subsequent failure rates and failure-free survival and test for association with biopsy positivity and treatment arm.

QOL scores will be calculated in accordance with established scoring methods for each instrument. Descriptive summaries of scores at baseline and each subsequent follow up will include median and range, means and standard deviations. Where criteria for clinically meaningful differences have been established, we will also categorize changes in these scores (computed by subtracting baseline from subsequent score) as indicating improvement,

worsening, or no change and summarize these by counts and percentages. Comparison by treatment arm at baseline and at treatment completion will be based on t-test (average score) and Fisher's exact test (percent improved). Further analysis allowing for repeated measurement will be conducted using mixed models.

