3. 10-15% of men undergoing RT have Circulating DNA or tumor cells (CTC) that are related to an adverse treatment outcome.
4. Quality of life will not differ significantly between the treatment arms.
5. Prostate cancer-related anxiety will be reduced in the HTIMRT arm, because the patients will be aware that the dominant tumor will be targeted with higher radiation dose.

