1.4.2 Post-treatment Biopsy Tissue Assessments

Prostate biopsies after external beam radiotherapy have been studied fairly extensively; although, many prior series involved patients treated prior to the routine use of PSA and transrectal ultrasound-directed sextant (or higher) biopsies. The principal investigator has coordinated prostate biopsy assessments at two years after completion of treatment from two randomized trials, one from M.D. Anderson Cancer Center (29, 30) and one from Fox Chase Cancer Center.(2) Biopsy positivity in the M.D. Anderson Trial was associated with about a 50% risk of biochemical failure at 8-10 years after the biopsies were taken (2 yr after RT). From our analysis of the biopsies from Fox Chase Cancer Center (FCCC) protocol 02-602 (PI: [name]), preliminary data indicate that nearly 50% of patients had residual tumor cells in the prostate at 2 years and that when the tumor burden was high on one side of the prostate, this appeared to predispose to a greater incidence of biopsy positivity on that same side.(2) Such an association has implications in how to approach the treatment of prostate cancer with radiotherapy; increasing RT dose to high tumor burden areas should lead to reduced local persistence and, consequently biochemical failure rates.

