2.2. Secondary Objectives

- To evaluate the impact of an HT boost on acute and late toxicity.
- To evaluate the influence of HTIMRT to health-related quality of life (HRQOL), prostate cancer-specific anxiety and prostate cancer-specific QOL.
- To quantify biomarker expression in different prostate tumor regions, comparing specifically the functional MRI suspicious regions to those that are not suspicious.
- To evaluate the incidence and relationship of circulating free DNA and tumor cells to tissue biomarkers and prostate biopsy positivity at 2 years after completion of therapy.
- To record other biochemical failure, clinical failure and mortality endpoints.

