14.0 STATISTICAL CONSIDERATIONS

14.1 Overview

This is a two-arm randomized Phase III trial with the primary objective of determining whether MRI-guided hypofractionated radiotherapy (HTIMRT), as compared with standard dose fractionation (SIMRT), reduces the two-year post treatment biopsy failure rate in men receiving primary radiotherapy for favorable to high risk prostate cancer. Secondary objectives include comparison of HTIMRT and SIMRT with respect to acute and late occurring toxicity, quality of life, biochemical and clinical failure, and survival. Additionally, blood and biopsy tissue samples from study patients will provide data for various biomarker studies described in the Bankhead Coley Team Science project "Integrated biomarkers for individualized prostate cancer therapy".

A single stage design without interim analysis of the primary endpoint is proposed for this trial. It would not be practical or desirable to suspend accrual for an extended period of time to accommodate an interim assessment of the two year failure rate as would be needed to consider early stopping for efficacy or futility (lack of efficacy) based on the main study endpoint.

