14.2 Sample size, accrual rate and study duration

Study size is based on our primary objective of demonstrating that, compared to SIMRT, HTIMRT reduces the two year post treatment failure rate, by which we mean the proportion of patients with either biopsy failure or earlier evidence (within two years of treatment completion) of biochemical and/or clinical failure. (See definition in Section 9.1.) We expect the two-year failure rate in the standard fractionation arm to be 52.5%, representing the combined effect of a small rate of biochemical or clinical failure within two years, approximately 5%, and a relatively high rate of positive biopsy among the remaining 95% of patients, namely 50% ($0.05 + 0.95 \times 0.50 = 0.525$). This estimate is based on prior findings on randomized trials previously

organized by the PI. (75) Assuming equal allocation of patients to SIMRT and HTIMRT and sufficient follow-up to determine failure status at two years, a study size of 36 patients in each treatment arm provides 80% power to detect an absolute reduction of 30% in the two-year failure rate (biochemical, clinical, or biopsy), from 52.5% to 22.5%, using a one-sided Fisher's exact test with 5% significance level. To ensure a minimum of 72 study patients evaluable for the two year failure rate as our main study endpoint, we plan to enroll a total of 76 patients.

Based on an accrual rate averaging 2 patients per month, we plan to complete enrollment in 3.2 years. Patients will be followed for five years giving total study duration of 8.2 years. Analyses of some secondary endpoints, including acute toxicity, psychosocial parameters, biomarker distribution on ultrasound-guided biopsies, and initial MRI findings may be reported before the efficacy endpoints, including the primary endpoint. These secondary endpoints will be analyzed after all planned patients have been accrued, completed treatment and have a minimal potential follow-up of 3 months from the end of RT. The main efficacy endpoint requires less than five years follow up and will be performed after all patients have been assessed for two year post treatment failure status (2 yr. biopsy). Final efficacy analysis will be at the conclusion of study when patients have been followed for 5.25 years.

14.3 Definitions and endpoints:

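### The blanket one-sided 5% rule for arm comparisons states no direction for toxicity, general QOL or biomarker change, and cannot apply to the four-category biopsy test

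*Combined protocol and SAP*

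**What the plan says.** The general rule in Section 14.5 is "Statistical tests comparing treatment arms will be one-sided with 5% significance level". The rest of that sentence adds stratification where appropriate; that qualifier concerns stratification, not sidedness.

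**Direction available**
- Two-year failure rate: Section 14.2 sets out to show that "HTIMRT reduces the two year post treatment failure rate".
- Biopsy failure rate: Section 14.5 says it is estimated and compared in a similar way, so the direction carries over.
- Anxiety: hypothesis 5 in the opening Hypotheses list says "Prostate cancer-related anxiety will be reduced in the HTIMRT arm".
- Biochemical failure: implied only, in Section 1.4.2: "increasing RT dose to high tumor burden areas should lead to reduced local persistence and, consequently biochemical failure rates".

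**No direction**
- Toxicity: the objective in Section 2.2 is "To evaluate the impact of an HT boost on acute and late toxicity", and Section 14.5 says "toxicity rates will be compared by treatment arm using Gray's test".
- General quality of life: hypothesis 4 says "Quality of life will not differ significantly between the treatment arms". Section 14.5 nevertheless plans a t-test on mean scores and a Fisher test on percent improved, at baseline and at treatment completion.
- Biomarker change by arm: Section 14.5 names two-sample tests and no alternative.
- Two-year biopsy findings in four categories: compared by Fisher's exact test, with no ordering of the categories.
- Failure-free survival, prostate cancer mortality and overall survival: log-rank or Gray's test, with no alternative stated in Section 14.

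The two-sided statements in Section 14.5 concern confidence intervals, not tests.

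**The concern.** A one-sided test is defined only when its alternative is written down. Section 14.1 makes the omitted endpoints formal comparisons: "Secondary objectives include comparison of HTIMRT and SIMRT with respect to acute and late occurring toxicity, quality of life, biochemical and clinical failure". Toxicity and quality of life are what any gain in biopsy failure has to be weighed against.

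With the side unstated, one of two things happens. Either a side is fixed without a record in the plan, and a difference in the other direction cannot be declared; or the side is settled once data are in hand. The second is a practical possibility: Section 14.5 allows acute toxicity, psychosocial and biomarker results to be reported before the efficacy endpoints.

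**Working it through.** **1. The plan's own figure.** Section 14.2 gives 36 per arm, 52.5% vs 22.5%, one-sided Fisher at 5%, 80% power. The control rate is 0.05 + 0.95 x 0.50 = 0.525. Enumerating both binomial distributions and rejecting when the hypergeometric tail is at most 0.05 gives 80.3%. The figure is reproduced. This test has a stated direction, so nothing below changes it.

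**2. Where the tail is open.** For Gray's test on two arms the statistic is chi-square on 1 df. A one-sided 5% version uses its signed root, which corresponds to a cut-off of 1.645^2 = 2.71 on one chosen side; two-sided 5% uses 3.84. The plan gives neither the side nor the cut-off. The same gap applies to the t-tests and the 2x2 Fisher tests. An unordered 2x4 table has no tails at all, so stating a direction would not make its Fisher test one-sided.

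**3. Type I error if the side is chosen after the data.** For a symmetric statistic it is 2 x 5% = 10%; this covers the t-test and, approximately, Gray's test. A simulation of a Gray-type test gave 10.0-10.9% for equal true rates of 5% to 30%. It used 100,000 trials per scenario, 38 per arm (76/2), exponential onset, 5.25 years of follow-up and assumed competing death of 0%, 5% or 10%. It did not model subsequent therapy, which Table 14.5 also lists as a competing risk for toxicity.

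Fisher's test is conservative. Exact enumeration at 38 per arm, rejecting if either one-sided p-value is at most 0.05, gives:

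| Equal true rate (assumed) | Type I error |
|---|---|
| 5% | 1.3% |
| 12% | 4.3% |
| 20% | 5.7% |
| 30% | 6.3% |

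**4. Power for an excess of toxicity on HTIMRT.** Exact Fisher as a stand-in, 38 per arm. All rates are assumptions. The 12% is anchored only on the 8-year grade 2+ urinary rate that Section 1.5 cites from another series; the lower rates reflect Section 10.0, which describes acute grade 3-4 toxicity as rare.

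| SIMRT vs HTIMRT | One-sided, harm | Two-sided 5% |
|---|---|---|
| 12% vs 30% | 52% | 40% |
| 5% vs 15% | 26% | 16% |
| 12% vs 20% | 16% | 10% |
| 2% vs 10% | 19% | 9% |

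**5. Mean QOL at treatment completion.** With 38 per arm and 80% power, the t-test detects 0.576 SD one-sided (correct side) or 0.651 SD two-sided. Adjusting for baseline multiplies this by sqrt(1 - rho^2). At an assumed correlation of 0.5, 0.651 x sqrt(0.75) = 0.564 SD; at 0.4 it is 0.597 and at 0.6 it is 0.521. The 95% CI half-width for the difference is 1.993 x sqrt(2/38) = 0.457 SD unadjusted and 0.457 x sqrt(0.75) = 0.396 SD adjusted at 0.5. Section 5.1 already collects the baseline score.

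**The case against.** The best reply is that the rule was meant for efficacy only. Its sentence follows those on the timing of the efficacy analyses. Section 14.5 also repeats that the primary Fisher test is one-sided, which would be redundant if one rule governed everything, and then names the four-category Fisher test without a side. On that reading Gray's test and the 2x4 Fisher test default to their usual non-directional forms. This part stands: a reader might infer that all these tests are undefined however the rule is read, and the documents do not support that. What stays unstated on the efficacy reading is the sidedness of the t-tests and 2x2 Fisher tests, and the alpha. Against it, the sentence itself contains no such limit.

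A reader might also infer that the rule would leave real harm almost undetectable, since a Fisher test pointed at benefit rejects in 0.005% of trials at 12% vs 30%. No passage suggests testing toxicity for benefit, and Section 14.6 is concerned only with excess, so that figure should not be used as the size of the problem. Harm also stays visible in the tabulations and cumulative incidence estimates by arm and in the stopping guideline. However, that guideline compares each arm with fixed rates of 15% and 10%; it is not a between-arm test and gives no direction for one.

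Finally, an unadjusted t-test is valid in a randomized trial, and mixed models are already planned as further analysis. That is correct: the baseline adjustment is an improvement in precision, not the repair of an invalid test.

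**Conclusion.** The gap is real and confined to secondary analyses; it should be closed. Read literally, the one-sided rule leaves the rejection region open for toxicity, general QOL and biomarker change by arm, and cannot be applied to the four-category biopsy test. Read as an efficacy rule, it leaves a smaller gap.

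If the side is picked after the data, error is about 10% for Gray's test and the t-test. A reader might extend that doubling to every comparison, but Fisher's test stays at 1.3-6.3% over the assumed range. Where toxicity is rare or the excess small, power is low with either choice.

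The conclusion about the wording rests on the text alone. The power figures rest on assumed rates and correlations and on 38 patients per arm.

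**What to change.** **1. Replace the general sentence in Section 14.5 with an assignment by endpoint.**
- One-sided at 5%, alternative lower on HTIMRT: the two-year failure rate, the biopsy failure rate and post-baseline MAX-PC.
- Two-sided at 5%: toxicity, EPIC-SF12, biomarker change, the four-category biopsy comparison, and any comparison of arms at baseline. Baseline questionnaires precede randomization, so a benefit alternative has no meaning there.
- Time-to-event efficacy endpoints: either write down the alternative (fewer events on HTIMRT) or test two-sided. The documents state no direction for survival, so the sponsor has to make this choice explicitly.
- Keep stratification where appropriate.

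This needs no new data and leaves the primary test and sample size alone. The cost is power for toxicity against a test pointed at harm: 40% instead of 52% by Fisher at the assumed 12% vs 30%.

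**2. Separately, compare mean QOL scores at treatment completion with baseline as a covariate**, by ANCOVA or the planned mixed model, and report the adjusted difference with a two-sided 95% CI. A non-significant test alone would not establish hypothesis 4. Keep the percent-improved comparison. At an assumed correlation of 0.5 the two-sided detectable difference falls from 0.65 to 0.56 SD. This gain stands on its own and does not pay for two-sided testing, because the same adjustment would take the one-sided figure to 0.576 x sqrt(0.75) = 0.50 SD.

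### No named between-arm test isolates late toxicity: Gray's test counts only the first grade 2+ or 3+ event from start of treatment, so acute grade 2+ events can dilute a late difference (cheap improvement)

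*Combined protocol and SAP*

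**What the plan says.** Two places set the objective. Section 2.2 reads "To evaluate the impact of an HT boost on acute and late toxicity", and Section 14.1 makes it a comparison of arms: "Secondary objectives include comparison of HTIMRT and SIMRT with respect to acute and late occurring toxicity". Section 9.1 defines the two periods, divided at three months after treatment completion.

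Section 14.5 then provides the following for graded toxicity:

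- A descriptive table: "detailed tabulation of acute and late occurring toxicity by type and grade, both overall and by treatment arm". No test is attached.
- A time-to-event analysis: "we will estimate the cumulative incidence (from start of treatment) of grade 2+ and 3+ genitourinary (GU) toxicity", and likewise for GI. On this analysis "toxicity rates will be compared by treatment arm using Gray's test". Table 14.5 has one toxicity row, counts the earliest event, and does not split by period.
- Cumulative incidence at chosen times: "cumulative incidence rates will be reported for selected times with corresponding 2-sided 95% confidence intervals".
- An early report that may cover "analyses of some secondary endpoints, including acute toxicity", once every patient has at least 3 months of potential follow-up after RT. It names no acute endpoint and no test.
- A general rule: "Statistical tests comparing treatment arms will be one-sided with 5% significance level".

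Section 14.6 does separate acute from late grade 3+ toxicity, but it judges each arm against a fixed threshold (15% acute, 10% late) and does not compare the arms.

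**The concern.** The objective has two parts and the named test has one. Once a man has an acute grade 2+ GU event, he has had his event in the GU analysis, and a later grade 2+ GU event does not enter Gray's test. The experimental component is a dose escalation to part of the prostate, so whether late toxicity rises is a central safety question. A late grade 2+ difference can be diluted in the pooled test, and a positive pooled test does not say which period produced it. As written, the plan would answer the late part of the objective only descriptively.

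**Working it through.** **The plan's own figures.** No power is stated for toxicity. The stated power for the primary endpoint (36 per arm, 52.5% v 22.5%, one-sided 5% Fisher's exact test) is 80%. Exact enumeration gives 80.3%, so it reproduces. The same method is used below.

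**Inputs from the documents**
- 38 per arm: 76 / 2 (Section 14.2).
- One-sided 5% tests (14.5). The direction for toxicity, more with HTIMRT, is assumed.
- GU anchor 12% and GI anchor 1.6%: 8-year grade 2+ urinary toxicity and rectal bleeding (Section 1.5). Neither is stated to be late-only.

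**Assumed.** All acute rates, the late HTIMRT rates (30% GU, 10% GI), independence of acute and late events, and use of the Section 1.5 figures as late control rates.

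**Formula.** First-event risk = a + (1 − a) × late risk. With equal a in both arms the gap is (1 − a) × (late HTIMRT − late SIMRT). Power is the sum of binomial probabilities over all tables with one-sided Fisher p ≤ 0.05.

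**GU, late 12% v 30%, equal acute risk**

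| Acute rate, both arms | First-event risk, SIMRT v HTIMRT | Gap (points) | Power |
|---|---|---|---|
| Late-only comparison | 12.0% v 30.0% | 18.0 | 52% |
| 10% | 20.8% v 37.0% | 16.2 | 38% |
| 20% | 29.6% v 44.0% | 14.4 | 30% |
| 40% | 47.2% v 58.0% | 10.8 | 16% |
| 60% | 64.8% v 72.0% | 7.2 | 12% |

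**Dependence.** Suppose men with acute toxicity have twice the late risk and the overall late rates stay at 12% v 30%. At acute 20% the risks are then 28.0% v 40.0%, a gap of 12.0 points instead of 14.4. Power is 33%, 23% and 10% at acute 10%, 20% and 40%.

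**The boost also raises acute toxicity (late still 12% v 30%)**

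| Acute, SIMRT v HTIMRT | First-event risk | Pooled power (late-only 52%) |
|---|---|---|
| 40% v 50% | 47.2% v 65.0% | 37% |
| 20% v 30% | 29.6% v 51.0% | 52% |
| 10% v 20% | 20.8% v 44.0% | 63% |
| 20% v 40% | 29.6% v 58.0% | 74% |

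**Time-to-event check.** Fisher's test stands in for Gray's test above. A simulated one-sided log-rank test (Gray's test with no competing events; 38 per arm, 4,000 trials per case; acute onset uniform over 0–0.4 year, late onset over 0.4–5.25 years) shows the same pattern. Late-only power is 61–64%, and pooled power is 44%, 32%, 18% and 11% at equal acute rates of 10%, 20%, 40% and 60%.

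**Grade 3+.** Section 10.0 calls acute grade 3 or 4 toxicity rare. At an assumed 3% acute rate, 0.97 × 18.0 = 17.5 points and power goes from 52% to 47%. The planned grade 3+ test is already close to a late test.

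**GI grade 2+.** For late 1.6% v an assumed 10%, late-only power is 21%, and first-event power at acute 20% is 11%. For a doubling from 1.6% late-only power is 0.4%. Here the gain is in estimation, not in testing.

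**Precision (Wald, 1.96 × SE, 38 per arm).** The 95% interval for the late difference is about ±18 points for GU at 12% v 30%, and ±10 points for GI at 1.6% v 10%.

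**The case against.** The strongest reply is that the period-specific information is not lost. The plan tabulates acute and late toxicity by type, grade and arm, and gives cumulative incidence at selected times with intervals. With about 38 men per arm, descriptive reporting by period is defensible. This stands in part: a reader of the trial report will see which period differs. But the incidence curves are still first-event curves, and a table without a comparison is less than the objective in 14.1 asks for.

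A second reply is that pooling is not generally worse. That is correct: in three of the four illustrations where acute toxicity also rises, the pooled test is as strong as the late-only test or stronger. The planned test should stay.

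Third, every effect size is assumed. The documents give no acute grade 2+ rate and no HTIMRT late rate, and if the 12% figure already includes acute events the control risk above counts them twice. The direction of the dilution under equal acute risk is arithmetic; its size is not established.

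A reader might infer that the plan has no analysis of either period. The documents do not support that. Section 9.1 lists acute and late toxicity as separate endpoints, and an acute analysis is planned with its test unnamed. A reader might also infer that an acute benefit of the boost could cancel late harm in the pooled test. One can construct this: acute 55% v 40% with late 12% v 36% gives 60.4% v 61.6%, power 4% against 73% late-only. Nothing in the documents suggests that the boost would lower acute toxicity while tripling late toxicity, so the point does not rest on this case.

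**Conclusion.** The point holds as a low-cost improvement, not as an error in a stated figure. No named between-arm test isolates late toxicity, although comparing the arms on it is a stated objective. The consequence is largely confined to grade 2+. With equal acute risk, independent of late risk, the late gap is multiplied by (1 − a). In the GU illustration power drops from 52% to between 38% and 12% for acute rates of 10% to 60%. The size depends on assumed rates and on independence. Positive dependence makes the dilution worse, while an acute effect in the same direction can remove or reverse the loss of power. Confidence is high that no late test is named, and much lower about the magnitude.

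**What to change.** Keep the planned curves and Gray's test, and add two items to 14.5.

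1. **Late grade 2+ GU and GI.** Estimate cumulative incidence from 3 months after RT completion, with all men still in follow-up at risk whatever their acute history, and competing risks as in Table 14.5. Use Gray's test and give the between-arm difference with a 95% interval. State that events are new onsets, as in 14.6. Because 9.1 speaks of toxicity occurring after three months, which is wider than new onset, report acute toxicity persisting at 3 months separately by arm.
2. **Acute grade 2+ GU and GI.** In the acute report already planned, give the proportions up to 3 months after RT by arm, with Fisher's exact test and the difference with a 95% interval.

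Give grade 3+ by period as estimates only.

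The cost is SAP wording: no new patients, visits or data. There are four more secondary comparisons (2 periods × GU/GI) beside the four planned (GU/GI × grade 2+/3+). They should be labelled supportive and unadjusted: for independent full-size 5% tests, the chance of at least one false positive rises from 1 − 0.95⁴ = 19% to 1 − 0.95⁸ = 34%. Power is modest for GU and very low for GI. The late curve is conditional on being in follow-up at 3 months, and persisting acute toxicity does not enter the late test, which is why it is reported separately.
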